9.1.2.2. Summary Measure

The change in the mean daily OCS dose from Week 0-4 to each 4-week period (Week 4-8, Week 8-12, Week 12-16 and Week 16-20).

9.1.2.3. Strategy for Intercurrent (Post-Randomization) Events

The treatment effect to be estimated (estimand) will be the ‘treatment policy’ effect of initial randomised treatment. A treatment policy strategy will be used for the intercurrent event of discontinuation of study medication. For subjects withdrawing prematurely from the study, all data up to the time of study withdrawal will be used to calculate the daily OCS (prednisone or equivalent) dose. Subjects that withdraw from the study prior to each 4-week period will not be included in the summary statistics for that 4-week period.

9.1.2.4. Statistical Analyses / Methods

Summary statistics for mean daily OCS (prednisone or equivalent) dose for Week 0-4, Week 4-8, Week 8-12, Week 12-16 and Week 16-20 will be presented, including change in the mean daily OCS dose.

The summary statistics to be reported for each four-week period are: minimum, maximum, mean, standard deviation and sample size (n). The same summary statistics will be reported for the change in mean daily OCS.

9.1.3. Proportion of participants who achieve a mean daily OCS (prednisone or equivalent) dose of 7.5mg or less during Weeks 16-20

9.1.3.1. Endpoint / Variables

Subjects who achieve a mean daily OCS (prednisone/prednisolone or equivalent) dose of 7.5mg or less during each four-week period (Week 0-4, Week 4-8, Week 8-12, Week 12-16 and Week 16-20) will be identified from the concomitant medications results, as defined in Section 13.4.4.

9.1.3.2. Strategy for Intercurrent (Post-Randomization) Events

The treatment effect to be estimated (estimand) will be the ‘treatment policy’ effect of initial randomised treatment. A treatment policy strategy will be used for the intercurrent events of discontinuation of study medication. For subjects withdrawing prematurely from the study, all data up to the time of study withdrawal will be used to calculate the mean daily OCS (prednisone or equivalent) dose and derive the above endpoint. Subjects that withdraw from the study prior to each 4-week period will not be included in the summary statistics for that 4-week period.

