9.1.2. Change in mean daily OCS dose from Weeks 0-4 to Weeks 16-20

9.1.2.1. Endpoint / Variables

The mean daily OCS (prednisone or equivalent) dose for each 4 week period (Week 0-4, Week 4-8, Week 8-12, Week 12-16 and Week 16-20) for each subject will be calculated as the sum of the daily doses of OCS during each period divided by the total number of days, 28. For each subject, the prednisone equivalent daily dose for each day will be determined as described in Section 13.4.4.

Subjects withdrawing from the study prematurely will have mean daily OCS (prednisone or equivalent) dose calculated using available data up to study withdrawal date only (divided by the number of days for which there is available data).

The change in the mean daily OCS dose from Week 0-4 to Week 16-20 will be calculated for each subject as the mean daily OCS dose for Week 16-20 minus the mean daily OCS dose for Week 0-4. The change in the mean daily OCS dose from Week 0-4 to each 4-week period (Week 4-8, Week 8-12 and Week 12-16) will be calculated using the same formula. The change in mean daily OCS dose will be summarised separately for a) all subjects and b) for subjects with a mean Week 0-4 OCS dose > 0mg.

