9.1.4.2. Strategy for Intercurrent (Post-Randomization) Events

The treatment effect to be estimated (estimand) will be the ‘treatment policy’ effect of initial randomised treatment. A treatment policy strategy will be used for the intercurrent events of discontinuation of study medication. For subjects withdrawing prematurely from the study, all data up to the time of study withdrawal will be used to calculate the mean daily OCS (prednisone or equivalent) dose and derive the above endpoint. Subjects that withdraw from the study prior to each 4-week period will not be included in the summary statistics for that 4-week period.

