Deflazacort	0.83
Hydrocortisone	0.25
Methylprednisone	1.25
Meprednisone	1.25
Prednisone	1
Prednisolone	1
Prednisone acetate	1
Triamcinolone	1.25

¹Budesonide has negligible systemic exposure and will be classed as “Other HES therapy” rather than oral corticosteroid therapy.

- Where the frequency of the recorded corticosteroid dose is not once daily, the following calculations will be used to determine the daily dose.

Medication Frequency	Daily Dose Equivalent
BID	2 x dose
TID	3 x dose
QID	4 x dose
QOD	dose / 2
2XWK	(2 x dose) / 7
3XWK	(3 x dose) / 7
4XWK	(4 x dose) / 7
5XWK	(5 x dose) / 7

Mean Daily OCS Dose
Change in the mean daily OCS dose from Weeks 0-4 to Weeks 16-20

 The mean daily OCS dose for weeks 0-4 will be calculated as $\frac{\textit{Sum of daily OCS dose for weeks 0 - 4}}{28}$ The mean daily OCS dose for weeks 16-20 will be calculated as $\frac{\textit{Sum of daily OCS dose for weeks 16 - 20}}{28}$ The change in the mean daily OCS dose from Weeks 0-4 to Weeks 16-20 will be the difference of mean daily OCS dose for weeks 16-20 minus mean daily OCS dose for weeks 0-4

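### The formula cited for the OCS responder endpoints (SAP 13.4.4) omits the divisor rule for withdrawers in SAP 9.1.2.1, and the proportions over time rest on a changing denominator with no supportive analysis

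*SAP*

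**What the plan says.** Two places in the SAP define the mean daily OCS dose for a four-week period.

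- **Section 9.1.2.1** covers all five periods. The summed daily doses are "divided by the total number of days, 28". For participants who leave the study early, only data up to withdrawal are used, "divided by the number of days for which there is available data".
- **Section 13.4.4** gives formulas for Weeks 0-4 and Weeks 16-20 only. The line beginning "The mean daily OCS dose for weeks 16-20 will be calculated as" is followed by the sum over 28. Participants who withdraw are not mentioned.

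The responder endpoints refer to the second place. Section 9.1.3.1 (mean dose of 7.5 mg or less) says that achievers "will be identified from the concomitant medications results, as defined in Section 13.4.4", and 9.1.4.1 (reduction of at least 50%) does the same. Section 9.1.3.2 adds that "all data up to the time of study withdrawal will be used to calculate the mean daily OCS (prednisone or equivalent) dose", but names no divisor.

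For participants who left before a period began, 9.1.3.2 states: "Subjects that withdraw from the study prior to each 4-week period will not be included in the summary statistics for that 4-week period". Section 9.1.4.2 has the same rule. Tables 3.7 and 3.8 present both proportions over time on the Safety population. No sensitivity analysis is planned for either.

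**The concern.** A programmer who follows the cross-reference from the responder sections finds one mean-dose formula, and it always divides by 28. Applied to a participant seen for only part of a period, that has the same arithmetic effect as setting the unseen days to 0 mg. An unchanged dose then looks like a reduction, and the same participant is a success under one section and a failure under the other.

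The exclusion rule is a separate matter. Each period's proportion is computed on those still in the study, so a rise from Weeks 0-4 to Weeks 16-20 can partly reflect who has left. The proportion at 7.5 mg or less in Weeks 16-20 is one of three exploratory efficacy endpoints listed in the protocol, and the 50% endpoint was added in SAP 2.4. With 80 to 120 participants randomised in the feeder study, a handful of participants is visible in a percentage.

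**Working it through.** The documents give no expected responder rate, withdrawal rate or sample size for this extension, so there is no planned figure to reproduce. Inputs from the SAP are the 28-day period, the 7.5 mg and 50% thresholds, and the two divisors. Assumed inputs are a constant dose within the period, group sizes, withdrawal rates and success rates.

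**1. Divisor, for dose D observed on k of 28 days**

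13.4.4 as written: D × k / 28. Section 9.1.2.1 for a withdrawer: D × k / k = D.

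Example: D = 20 mg/day, k = 10, Week 0-4 mean of 20 mg.

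- Divided by 28: 200/28 = 7.14 mg, so at or below 7.5 mg. Reduction (20 − 7.14)/20 = 64%. A success on both endpoints.
- Divided by available days: 200/10 = 20 mg. Reduction 0%. A failure on both.

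An unchanged dose passes the 7.5 mg threshold under the 28-day divisor when k ≤ 7.5 × 28 / D = 210/D:

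| Dose (mg/day) | Counted as success if observed days are at most | Mean with divisor 28 (mg) | Mean on available days (mg) |
|---|---|---|---|
| 10 | 21 | 7.50 | 10 |
| 15 | 14 | 7.50 | 15 |
| 20 | 10 | 7.14 | 20 |
| 30 | 7 | 7.50 | 30 |

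For the 50% endpoint, an unchanged dose gives an apparent reduction of 1 − k/28: 75% at 7 days, 50% at 14 days and 46% at 15 days. Any unchanged dose therefore counts as a success at 14 or fewer observed days.

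Effect of one such case, assuming 90 in the denominator and 45 true successes: 45/90 = 50.0% becomes 46/90 = 51.1%, or 1.1 points.

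**2. Denominator**

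Observed-case: s/(N − W). Fixed denominator with leavers counted as not achieving: s/N. Taking N = 100:

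| Withdrawn before the period (W) | Successes (s) | Observed-case | Fixed denominator | Gap (points) |
|---|---|---|---|---|
| 5 | 38 | 40% | 38% | 2 |
| 5 | 57 | 60% | 57% | 3 |
| 10 | 36 | 40% | 36% | 4 |
| 10 | 54 | 60% | 54% | 6 |
| 20 | 32 | 40% | 32% | 8 |
| 20 | 48 | 60% | 48% | 12 |

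**3. Direction against the whole-group rate**

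With 10% withdrawn and 50% success among those who remain, the whole-group rate is 0.9 × 50% + 0.1 × (success rate in withdrawers).

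| Success in withdrawers | Whole-group rate | Observed-case 50% is |
|---|---|---|
| 0% | 45.0% | 5.0 points too high |
| 25% | 47.5% | 2.5 points too high |
| 50% | 50.0% | correct |
| 75% | 52.5% | 2.5 points too low |

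**The case against.** The best defence is that 9.1.2.1 already contains the right rule. It states the general divisor and then an express exception for withdrawers, and 13.4.4 does not revoke it. The reference to 13.4.4 may be meant only for turning concomitant-medication records into daily doses, which is how 9.1.2.1 itself uses it. The 13.4.4 formulas sit under the change endpoint and cover two periods, while the responder endpoints need up to five. The 0 mg rule in 13.4.4 concerns days when a subject is not receiving OCS; it does not address days after withdrawal. All of this stands. It means that the SAP has not adopted a rule of dividing partial periods by 28, although a reader might infer one. It does not remove the problem: the section that the responder endpoints cite contains one mean-dose formula, without the exception.

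A reader might also infer that the treatment-policy label is wrong. The SAP applies that strategy to stopping study medication. Protocol 8.1 asks those participants, where possible, to stay in the study, and while they do they remain in the denominator. Leaving the study is a missing-data question, and counting leavers as failures would not be closer to treatment policy.

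A third tempting reading is that withdrawal inflates the success rate. That is certain only when compared with counting leavers as not achieving. Against the whole-group rate it requires leavers to do worse, which is plausible but nowhere shown.

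Finally, the endpoints are exploratory and descriptive, disposition is tabulated (Tables 1.1 and 1.3), and Protocol 7.7 gives participants a reason to remain to Week 20 by tying expanded access to that time point.

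**Conclusion.** The point holds as an inconsistency with a checkable consequence. If the 13.4.4 formula is programmed as written, a participant who withdraws part-way through Weeks 16-20 on an unchanged dose can be counted as a success on one or both responder endpoints. Each such case adds about one percentage point with 90 in the denominator. This arises only for withdrawal within the analysed period and only under the 28-day divisor. Withdrawal before the period removes the participant and creates no success.

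The exclusion of prior withdrawers is a legitimate observed-case summary, but it leaves the trend over periods resting on different sets of participants with nothing to show how much that matters. The difference from a fixed denominator is 2 to 12 points over withdrawal of 5-20% and success of 40-60%, which are assumptions and not figures from the documents. Whether the reported proportion is too high depends on how leavers were doing. With no hypothesis test attached, the matter affects how the results are described and does not bear on the primary safety objective.

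**What to change.** 1. In SAP 13.4.4, divide by the number of days with available data for participants who withdraw, as 9.1.2.1 does. State that this applies to every four-week period and to both responder endpoints, and cite 9.1.2.1 from 9.1.3.1 and 9.1.4.1.
2. Keep the observed-case proportions in Tables 3.7 and 3.8. Beside them, add a supportive analysis on a fixed denominator: all Safety participants for the 7.5 mg endpoint, and all with a Week 0-4 mean OCS dose above 0 mg for the 50% endpoint. Count those with no data in the period as not achieving.

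The first change is a line of text and the matching code. The second costs one extra table. Neither needs new data. The supportive figure will be lower than the observed-case one whenever leavers are excluded from a period with any successes, and it is conservative if some of them were doing well; for that reason it should not replace the observed-case figure. A minimum number of observed days is a matter of judgement for exploratory endpoints and is not needed to resolve this point.

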9.1.3.3. Statistical Analyses / Methods

The number and percentage of subjects who achieve a mean daily OCS (prednisone/prednisolone or equivalent) dose of 7.5mg or less during Week 16-20 will be presented. The number and percentage of subjects who achieve a mean daily OCS dose of 7.5mg or less during Week 0-4, Week 4-8, Week 8-12 and Week 12-16 will also be tabulated.

9.1.4. Proportion of participants who achieve a mean daily OCS (prednisone or equivalent) reduction of 50% or more during Weeks 16-20

9.1.4.1. Endpoint / Variables

Subjects who achieve a mean daily OCS (prednisone/prednisolone or equivalent) reduction of 50% or more throughout each four-week period (Week 4-8, Week 8-12, Week 12-16 and Week 16-20) will be identified from the concomitant medications results, as defined in Section 13.4.4. This endpoint will be summarised for subjects with a mean Week 0-4 OCS dose > 0mg only.

9.1.4.2. Strategy for Intercurrent (Post-Randomization) Events

The treatment effect to be estimated (estimand) will be the ‘treatment policy’ effect of initial randomised treatment. A treatment policy strategy will be used for the intercurrent events of discontinuation of study medication. For subjects withdrawing prematurely from the study, all data up to the time of study withdrawal will be used to calculate the mean daily OCS (prednisone or equivalent) dose and derive the above endpoint. Subjects that withdraw from the study prior to each 4-week period will not be included in the summary statistics for that 4-week period.

9.1.4.3. Statistical Analyses / Methods

The number and percentage of subjects who achieve a mean daily OCS (prednisone/prednisolone or equivalent) dose of reduction of 50% or more during Week 16-20 will be presented. The number and percentage of subjects who achieve a mean daily OCS dose of reduction of 50% or more during Week 4-8, Week 8-12 and Week 12-16 will also be tabulated.

10. PHARMACOKINETIC ANALYSES

10.1. Primary Pharmacokinetic Analyses

10.1.1. Endpoint / Variables

10.1.1.1. Drug Concentration Measures

Refer to [Appendix 5: Data Display Standards & Handling Conventions \(Section 13.3.3 Reporting Standards for Pharmacokinetic Data\)](#).

No pharmacokinetic analyses are planned for this study. However Pharmacokinetic samples for determination of mepolizumab plasma concentrations will be collected at the same time as immunogenicity samples to help interpretation of immunogenicity impact. Pharmacokinetic concentrations will be summarised by previous treatment group from study 200622, immunogenicity status and visit. All pharmacokinetic concentration data will be listed.

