9.5. Pharmacokinetics

- Blood samples for determination of mepolizumab plasma concentration will be collected prior to dosing at the timepoints indicated in SoA. The actual date and time of each blood sample collection will be recorded.
- Processing, storage and shipping procedures are provided in the laboratory manual.

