2.2. Study Design

Overview of Study Design and Key Features	

↑: Mepolizumab treatment (300mg SC per administration) V: Visit ^: Participants who continue with mepolizumab treatment via MHE104317/MHE112562 after Study 205203 will have the last assessment on Week 20 (Visit 6). #: Participants who do not continue with mepolizumab via MHE104317/MHE112562 after Study 205203 will have additional follow-up 12 weeks after the last dose (Visit 7).
	
Design Features	
 Multi-centre, open-label extension, 20-week treatment period, safety study of mepolizumab in adolescent and adult participants with HES who took part in the phase 3 study 200622. Visit 1 for study 205203 is the exit visit (32 weeks after randomisation) for study 200622. Investigators will be blinded to the blood eosinophil count from the sample obtained at visit 1 (first dosing visit), in order to maintain the blinding of study 200622, after which eosinophil counts will be unblinded starting from visit 2. Investigators may adjust the participants' background HES therapy per standard of care starting at visit 2 (approximately 4 weeks after the first dose of open-label mepolizumab). Participants who withdraw from study treatment prematurely should continue in the study per protocol until 20 weeks from first dose of open-label mepolizumab. Participants who complete assessments at visit 6 (week 20) may continue with mepolizumab treatment via MHE104317/MHE112562, where local regulation permits. Study participants who do not continue with MHE104317/MHE112562 will have an additional follow-up assessment 12 weeks after the last dose of mepolizumab.
Dosing	
 300 mg SC mepolizumab every 4 weeks (5 administrations) while continuing their HES therapy. The final dose of study treatment will be administered at Visit 5 (Week 16) with completion of the study treatment period achieved at the next 4-weekly visit.

Overview of Study Design and Key Features	
Time & Events	
 See Appendix 1: Schedule of Activities
Treatment Assignment	
 All participants are assigned to 300mg SC mepolizumab. Between 80 and 120 participants will be randomised in study 200622. Those participants who complete required assessments for 32 weeks starting from randomisation may be evaluated for eligibility to study 205203.

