11.1.4. Strategy for Intercurrent (Post-Randomization) Events

For subjects withdrawing prematurely from study treatment, only the endpoint values up to and including 28 days after the last dose of study treatment will be included in the analysis ('while on treatment' estimand).

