13.3.2. Reporting Standards

General	

 All data displays (Tables, Figures & Listings) will use the term “Subject” rather than “Participant” which reflects CDISC and GSK Data Display Standards terminology. The current GSK Integrated Data Standards Library (IDSL) will be applied for reporting, unless otherwise stated (IDSL Standards Location: https://spope.gsk.com/sites/IDSLLibrary/SitePages/Home.aspx): 
 4.03 to 4.23: General Principles 5.01 to 5.08: Principles Related to Data Listings 6.01 to 6.11: Principles Related to Summary Tables 7.01 to 7.13: Principles Related to Graphics Do not include subject level listings in the main body of the GSK Clinical Study Report. All subject level listings should be located in the modular appendices as ICH or non-ICH listings 	
Formats	

 GSK IDSL Statistical Principles (5.03 & 6.06.3) for decimal places (DPs) will be adopted for reporting of data based on the raw data collected but may be adjusted to a clinically interpretable number of DPs. 	
Planned and Actual Time	

 Reporting for tables, figures and formal statistical analyses: 
 Planned time relative to dosing will be used in figures, summaries, statistical analyses and calculation of any derived parameters, unless otherwise stated. The impact of any major deviation from the planned assessment times and/or scheduled visit days on the analyses and interpretation of the results will be assessed as appropriate. Reporting for Data Listings: 
 Planned and actual time relative to study drug dosing will be shown in listings (Refer to IDSL Statistical Principle 5.05.1). 	

 • Unscheduled or unplanned readings will be presented within the subject’s listings. • Visits outside the protocol defined time-windows (i.e. recorded as protocol deviations) will be included in listings, summaries and statistical analyses. 	
Unscheduled Visits	

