13.3.3. Reporting Standards for Pharmacokinetic Data

Pharmacokinetic Concentration Data	
Descriptive Summary Statistics, Graphical Displays and Listings	Refer to IDSL PK Display Standards. Refer to IDSL Statistical Principle 6.06.1. Note: BLQ concentration values will be imputed as per GUI_51487 for descriptive summary statistics only.

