13.8.9. Pharmacokinetic Tables

Pharmacokinetic: Tables					
No.	Population	IDSL / Example Shell	Title	Programming Notes	Deliverable [Priority]
4.1.	Safety	PK01	Summary of Plasma Mepolizumab Concentration-Time Data (by previous treatment group from study 200622 and by immunogenicity status)		SAC

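### The PK summary by immunogenicity status has no time-since-last-dose condition, so Week 20 samples taken after early stopping are pooled with 4-week troughs

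*SAP*

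**What the plan says.** SAP 10.1.1.1 plans no PK analysis as such. Samples are taken alongside the immunogenicity samples "to help interpretation of immunogenicity impact", and the summary rule is: "Pharmacokinetic concentrations will be summarised by previous treatment group from study 200622, immunogenicity status and visit". Table 4.1 in SAP 13.8.9 is titled "Summary of Plasma Mepolizumab Concentration-Time Data (by previous treatment group from study 200622 and by immunogenicity status"). It uses the Safety population, has no on-treatment qualifier in its title, and its programming note is empty. SAP 13.3.3 gives one handling rule in its own text, "BLQ concentration values will be imputed as per GUI_51487 for descriptive summary statistics only", and otherwise points to external display standards. SAP 13.3.2 sets the general time basis: "Planned time relative to dosing will be used in figures, summaries, statistical analyses and calculation of any derived parameters, unless otherwise stated".

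On follow-up after stopping, SAP 2.2 says: "Participants who withdraw from study treatment prematurely should continue in the study per protocol until 20 weeks from first dose of open-label mepolizumab". The schedule of activities (Protocol section 2) places PK samples at Visits 1 and 6, at the WD visit and at Visit 7. SAP 13.2 defines time off treatment for participants who reach Week 20 more than 28 days after their last dose, so the situation is foreseen.

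Eosinophils are treated differently. For participants who stop treatment early, SAP 11.1.4 says that "only the endpoint values up to and including 28 days after the last dose of study treatment will be included in the analysis", and the eosinophil tables and figures are titled as on-treatment displays.

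**The concern.** A drug concentration depends directly on time since the last dose. Protocol 5.1 intends Visit 6 to fall 4 weeks after the last dose, and that holds only for participants who received the Week 16 dose. For the others, Visit 6 is an off-treatment sample of variable age, yet by nominal visit it enters the same cell.

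Visit 1 has a parallel problem in the previous-mepolizumab group. Entry route (ii) in Protocol 6.1 admits participants who stopped 200622 treatment early but stayed to 32 weeks. Their Visit 1 sample is older than the roughly 4 weeks since last dose described in Protocol Appendix 2.

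The PK samples exist to put the ADA result into context (Protocol 10.3.2). If a very small ADA-positive cell contains one participant who stopped dosing weeks earlier, its low mean could be read as antibody-driven loss of exposure when the cause is stopped dosing.

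The eosinophil rule has a related timing gap. The WD visit is allowed at 4 weeks ± 1 week after the last dose, but the cut-off is day 28, so a compliant WD sample on days 29-35 is dropped.

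**Working it through.** The documents contain no figure to reproduce here: there is no sample size calculation, half-life or expected stopping rate. The timing follows from the schedule. The concentrations are illustrations under stated assumptions.

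**Inputs from the documents.** Doses at Weeks 0, 4, 8, 12 and 16, and visit windows of ± 1 week (Protocol section 2). Parent-study size 80 to 120 (Protocol 5.2). ADA incidence 2% to 6% in the severe asthma studies (Protocol 3.3.1), used only as a planning range.

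**Assumptions.** Half-life of 14, 21 or 28 days with mono-exponential decay. Stopping rates of 5%, 10% or 20%, independent of ADA status.

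**1. Age of the Week 20 sample.** Days since last dose = 7 × (20 − week of last dose). Ratio to a 28-day trough = 2^(−(days − 28) / half-life).

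| Last dose | Days at Visit 6 | Ratio, 14 d | Ratio, 21 d | Ratio, 28 d |
|---|---|---|---|---|
| Week 16 | 28 | 1 | 1 | 1 |
| Week 12 | 56 | 0.25 | 0.40 | 0.50 |
| Week 8 | 84 | 0.06 | 0.16 | 0.25 |
| Week 4 | 112 | 0.016 | 0.06 | 0.125 |
| Week 0 | 140 | 0.004 | 0.025 | 0.06 |

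The first row agrees with the protocol's intended 4 weeks. Summing the contributions of all doses given leaves the ratios unchanged for the previous-mepolizumab group and makes them slightly lower for previous placebo (for example 0.226 instead of 0.25 for Week 8 at 28 days).

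**2. Size of the ADA-positive cells.** 80 × 0.02 = 1.6 and 120 × 0.06 = 7.2 participants in total, or 0.8 to 3.6 per previous-treatment group if split evenly. These counts assume that every randomised participant enters the extension, so for a given incidence they are upper bounds.

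**3. Effect of one stopper in an ADA-positive cell, no true ADA effect.** With ratio r and cell size n, the arithmetic mean becomes (n − 1 + r)/n of its true value and the geometric mean r^(1/n).

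- n = 3, last dose Week 8: arithmetic 0.69 to 0.75 (25-31% lower); geometric 0.40 to 0.63 (37-60% lower).
- n = 3, last dose Week 12: arithmetic 0.75 to 0.83 (17-25% lower); geometric 0.63 to 0.79 (21-37% lower).
- n = 5, last dose Week 8: 15-19% lower (arithmetic) or 24-43% lower (geometric).

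**4. Chance that it happens.** 1 − (1 − d)^n for stopping rate d. For n = 3: 14%, 27% and 49% at 5%, 10% and 20%. For n = 5: 23%, 41% and 67%. At d = 0 it is zero.

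**5. The opposite direction.** If 10% of ADA-negative participants had their last dose at Week 8, their arithmetic mean is 0.90 + 0.10r, which is 8-9% lower. The geometric mean is r^0.10, or 13-24% lower.

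**6. What limit the windows allow.** An in-window Week 16 dose falls on days 105-119 and an in-window Visit 6 on days 133-147, so the gap runs from 133 − 119 = 14 to 147 − 105 = 42 days. A last dose at Week 12 (days 77-91) gives 133 − 91 = 42 to 147 − 77 = 70 days. The ranges touch only at the extreme value of 42.

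**7. Eosinophils.** The WD window is days 21-35. Days 29-35 are 7 of those 15 days, or 47% if visits were spread evenly, which is an assumption.

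**The case against.** The strongest reply is that this is a descriptive table with safeguards. No PK hypothesis is tested. All concentrations are listed, listings show actual time relative to dosing, and SAP 13.3.2 promises to assess the impact of major timing deviations as appropriate. With a handful of ADA-positive participants, a careful reader can look up each one. This stands as a limit on severity. It does not repair the table, and a Visit 6 attended on schedule after stopping is not a deviation from planned assessment times.

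Second, the PK display standards cited in SAP 13.3.3 and the mock shells are not available. They may contain a rule, so the gap is established for the visible text only.

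Third, the cell is not fully settled. Protocol 8.1 labels the 20-week point for stoppers as Visit 7, whereas the schedule makes it Visit 6. After a last dose at Week 8 the two visits coincide, and no labelling rule is given. SAP 13.3.2 moves a WD sample to the next scheduled visit only if that visit is empty, so it does not displace an existing Week 20 value. These labels need reconciling, but none of this supplies an on-treatment rule.

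At Visit 1, exclusion criteria 6 and 8 in Protocol 6.2 remove some participants who stopped 200622 treatment early, but not all.

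A reader might go further and infer that the ADA primary endpoint is biased, or that a real ADA effect would be masked. The documents do not support either. ADA incidence does not use these concentrations, and masking would need a sizeable share of ADA-negative stoppers, for the modest arithmetic shift in step 5. A reader might also infer that a 28- or 35-day limit on every PK sample is the natural remedy. Step 6 shows that it could discard in-window Week 20 samples from participants who took all five doses.

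**Conclusion.** The point holds as a gap in the specification. Followed as written, Table 4.1 pools Week 20 samples nominally 8 to 20 weeks post-dose with 4-week troughs, in the comparison meant to interpret ADA. Visit 1 can mix in the same way for the previous-mepolizumab group. The SAP already applies an on-treatment principle to eosinophils, so the omission for PK is an inconsistency.

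The realistic risk is a spurious low mean in a very small ADA-positive cell. Its size rests on the assumed half-life, the assumed stopping rate and an ADA incidence borrowed from asthma. It is nil if nobody stops early, and the listings would let a reader trace it. The eosinophil window is a smaller, secondary point.

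**What to change.** In SAP 10.1.1.1 and the Table 4.1 programming note:

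- Restrict the by-visit PK summary to on-treatment samples, defined by actual dates as no more than 42 days since the last mepolizumab dose (28 days plus both ± 1 week windows). This still excludes nominal 56-day samples. Alternatively, exclude only samples taken after treatment discontinuation, which leaves full-dose participants untouched.
- Show off-treatment samples, including Visit 7, in a separate row by time since last dose.
- Apply the same rule at Visit 1 for previous-mepolizumab participants, using the last 200622 dose. The 200622 visit windows are not in these documents, so check 42 days against them.
- State whether immunogenicity status is per visit or highest post-baseline, and which label a coinciding Visit 6 and Visit 7 sample takes.

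In SAP 11.1.4, allow 35 days for early stoppers so that in-window WD eosinophil samples are kept. The figure is 35 here because the WD window is counted directly from the last dose. Word it as a PD-specific allowance that leaves the SAP's 28-day on-treatment convention for adverse events unchanged.

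The cost is SAP wording, one derived variable (days since last dose), and a slightly smaller n in the Week 20 PK row. No new samples are needed. Protocol 9.5 already provides that "The actual date and time of each blood sample collection will be recorded", and Protocol 7.5 records dose dates. The last 200622 dose date must be brought across with the other parent-study data.
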